**Listing 5.88-1 Patients who received chemotherapy for progression/relapse – Safety Set (XX patients)**

Patient identification number	Inclusion date	Date of progression	Treatment for progression		
			Chemotherapy	Date	Description
XXXXX	XX/XX/XX	XX/XX/XXXX	Yes	XX/XX/XXXX	XXX

**Same listing for other treatment received by at least 1 patient (no listing will be provided if empty) :**

- Radiotherapy
- Monoclonal Antibody
- ...

**Table 5.88-4 Response according to Cheson 99 after treatment for progression/relapse – Safety Set**

	Safety Set N=XX
Progression/relapse	XX
Response	
Complete response	XX (XX.X%)
Unconfirmed complete response	XX (XX.X%)
Partial response	XX (XX.X%)
Stable disease	XX (XX.X%)
Progressive disease	XX (XX.X%)
Not evaluated	XX (XX.X%)

## 5.9 Extent of exposure

### 5.9.1 Cycles

**Table 5.9-1 Cycles performed – Safety set**

	Safety set N=XX
Cycle performed	
Cycle 1	XX (XX.X%)
Cycle 2	XX (XX.X%)
Cycle 3	XX (XX.X%)
Cycle 4	XX (XX.X%)

**Table 5.9-2 Number of cycles performed – Safety set**

	Safety set N=XX
Number of cycles performed	
N	XX
Missing	XX
Mean (SD)	XX.X (XX.XX)
Median	XX.X
Q1 ; Q3	XX ; XX
Min ; Max	XX ; XX

**Table 5.99.1-3 Treatment intake duration – Safety set**

	Safety set N=XX
Treatment intake duration (months)	
N	XX
Missing	XX
Mean (SD)	XX.X (XX.XX)
Median	XX.X
Q1 ; Q3	XX ; XX
Min ; Max	XX ; XX

Treatment intake duration is defined as the time between the 1st intake of any induction drugs and the last intake of any induction drugs.

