7 STUDY DESIGN

This study is a multicentric, single arm phase II trial to evaluate the efficacy of upfront obinutuzumab in mantle cell lymphoma patients treated by DHAP followed by autologous transplantation plus obinutuzumab maintenance then MRD driven maintenance.

Patients will be recruited over about 2 years and followed until 6.5 years after the last patient included.

The theoretical study dates (start / end) are:

- 1st patient included (FPFV): Q4 2016
- Last patient included (LPFV): Q3 2018
- Last patient followed for principal analysis: Q1 2025

It is expected about 83 patients to have 70 evaluable patients included in the study.

The duration of the treatment period is approximately:

- induction: 12 weeks for 4 cycles of chemotherapy
- conditioning regimen: 8 days
- maintenance : 3 years
- maintenance “on-demand” : 3 years

End of study is defined as the last visit of the last patient in follow-up planned by the protocol.

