10 TREATMENTS

10.1 Drugs description, storage, handling and administration

Drugs composing the DHAP and conditioning regimen for transplant are registered and are available at the hospital pharmacy.

Chemotherapy products are to be used according to summary of product characteristics.

Obinutuzumab is considered as investigational medicinal product (IMP) and will be supplied by Roche from induction to maintenance.

10.1.1 *Obinutuzumab: Description*

Obinutuzumab as know as GA101 is a humanized glycoengineered type II anti-CD20 monoclonal antibody that recognizes the CD20 antigen present on normal and malignant B cells and is being developed for the treatment of hematological malignancies including NHL and CLL.

10.1.2 *Obinutuzumab: Packaging*

Obinutuzumab is provided as a single-dose, sterile liquid formulation in a 50mL pharmaceutical grade glass vial containing a nominal 1000 mg of Obinutuzumab (G3 material). The formulated drug product consists of 25 mg/mL drug substance (G3) formulated in histidine, trehalose, and poloxamer 188. The vial-contains 41 mL (with 2.5% overfill).

10.1.3 *Obinutuzumab: Storage conditions*

The recommended storage conditions for the Obinutuzumab drug product are between 2°C to 8°C protected from light. Chemical and physical in-use stability for Obinutuzumab dilutions in 0.9% sodium chloride in the concentration range from 0.2 to 20mg/mL have been demonstrated for 24 hours at 2°C to 8°C and at ambient temperature and ambient room lighting. The prepared diluted product should be used immediately. If not used immediately, in-use storage times and conditions prior to use are the responsibility of the user and would normally not be longer than 24 hours at 2°C to 8°C. Obinutuzumab should not be frozen or shaken. Mix gently. All transfer procedures require strict adherence to aseptic techniques. Do not use an additional in-line filter due to potential adsorption.

10.1.4 *Obinutuzumab: Handlings*

Obinutuzumab should be given as a slow IV infusion. It should not be administered as an IV push or bolus. Obinutuzumab infusions should be made through a dedicated line. Isotonic 0.9% sodium chloride solution should be used as the infusion vehicle. Obinutuzumab will be administered at the flat dose of 1000mg.

Reconstituted Obinutuzumab drug product intended for IV infusion is prepared by dilution of the drug product into an infusion bag containing 0.9% sodium chloride, to the final drug concentration of 4 mg/mL.

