10.2 Treatment schedule and design

Upon completion of the required assessments in the screening phase and fulfillment of the eligibility criteria, eligible patients will be included and will enter in the treatment phase.

Patients with high tumor load may receive a pre-phase treatment of COP described below. The pre-phase therapy should be started after inclusion and after samples for MRD analysis.

Chemotherapy regimen	Dose	D1	D2	D3	D4	D5
Prednisolone	80 mg/m ²	X	X	X	X	X
Cyclophosphamide	750 mg/m ²	X				
Vincristine	1.4 mg/m ²	X				

10.2.1 *Induction treatment: GA-DHAP*

Patients will receive 4 cycles of GA-DHAP every 21 days.

*In case of toxicities related to cisplatin or according to the local investigator choice, carboplatinum AUC = 5 could be used instead of cisplatinum.

G-CSF administration is required during treatment cycles and stem cell collections.

10.2.1.1 Cycle 1

- Patients will receive their first Obinutuzumab infusion (1000 mg) on Day 1 (Cycle 1 Day 1) along with standard premedication. During Cycle 1, Obinutuzumab will also be administered on Days 8 and 15.
- Patients will be monitored for signs of acute tumor lysis syndrome (TLS)
- For patients treated with pre-phase, Cycle 1 has to be started 1 week after the end of the COP
- The products doses should be capped at 2m²

Chemotherapy regimen	Dose	D1	D2	D3	D4	D8	D15
Dexamethasone	40mg	X	X	X	X		
GA-101 IV	1000mg	X				X	X
Aracytine IV (every 12 hours)	2 g/m ²	X X					
Cisplatinum* IV	100 mg/m ²	X					

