10.5 Prophylactic measures

10.5.1 **Infusion-Related Reactions related to Obinutuzumab**

The most frequently observed adverse drug reactions (ADR) in patients receiving Obinuzumab were IRR; these occurred predominantly during the first infusion. The incidence and severity of infusion related symptoms decreased substantially with subsequent infusion.

See also section 10.1.5. *Administration* for the management of IRR

During induction treatment, dexamethasone should be administrated before the infusion of Obinutuzumab

If a patient experiences an IRR during the prior infusion, he should receive 100mg prednisolone or equivalent.

If a patient does not experience an IRR (grade ≥ 1) during the first infusion, the premedication for the infusions of maintenance can be omitted.

The first Obinutuzumab infusion should be administered to patient after premedication with oral analgesic/anti pyretic (e.g. 1000mg) and anti-histaminic drug (e.g. 50 mg diphenhydramine)

Grade 4 (life-threatening)	Stop infusion and discontinue therapy.
Grade 3 (severe)	Temporarily interrupt infusion and treat symptoms. Upon resolution of symptoms, restart infusion at no more than half the previous rate (the rate being used at the time that the IRR occurred) and, if patient does not experience any IRR symptoms, infusion rate escalation may resume at the increments and intervals as appropriate for the treatment dose
Grade 1-2 (mild and moderate)	Reduce infusion rate and treat symptoms. Upon resolution of symptoms, continue infusion and, if patient does not experience any IRR symptoms, infusion rate escalation may resume at the increments and intervals as appropriate for the treatment dose

10.5.2 ***Tumor Lysis Syndrome***

Patients who are considered to be a risk of TLS (e.g. patients with a high tumor burden or a high circulating lymphocyte count) should receive adequate tumor lysis prophylaxis with allopurinol (or adequate alternative) and hydration starting 12-24 hours prior to the infusion of Obinutuzumab.

10.5.3 ***Infection***

Obinutuzumab should not be administrated in the presence of an active infection.

Prophylaxis of infections is required for all patients during all the study treatment, in the discretion of the treating physician.

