### 3.2.3 Secondary safety endpoints

Summary of study drug administration including treatment duration and average dose will be displayed.

Number, frequency, reasons for premature treatment discontinuation and study discontinuation will be summarized.

Adverse events, clinical laboratory measurements will be described.

AEs will be classified using the latest version of Medical Dictionary for Drug Regulatory Activities (MedDRA) coding system at the time of database lock. The severity of the toxicities will be graded according to the National Cancer Institute (NCI) Common Terminology Criteria for Adverse Events (CTCAE) whenever possible. Subsets of AEs to be summarized include serious, NCI CTCAE grade severities, suspected treatment-related, and events that resulted in withdrawal of investigational product. The most severe grade of each preferred term for a patient will be utilized for summaries of adverse events by NCI CTCAE grade.

All AEs and SAEs will be described by system organ class and preferred term (a patient having the same event more than once will be counted only once) by period. Focus on AEs leading to death, AEs leading to discontinuation from treatment and AEs of special interest (i.e Tumor Lysis Syndrom) will also be displayed in a separate table and listing.

All deaths will be listed and summarized by cause of death and narratives of death will be also presented.

This endpoint will be performed on safety set (SS).

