### 3.4 Extent of exposure

- Treatment duration
- Total dose
- % planned dose

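### The SAP gives no time on obinutuzumab after induction: its only treatment-duration table ends at the last induction drug

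*SAP*

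**What the plan says.** SAP 3.2.3 (secondary safety endpoints), in the same terms as Protocol 15.1.2.2, states: "Summary of study drug administration including treatment duration and average dose will be displayed". SAP 3.4 lists "Treatment duration" as the first item of extent of exposure, with no restriction to a period.

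The study drug is obinutuzumab. Protocol 10.1 states: "Obinutuzumab is considered as investigational medicinal product (IMP) and will be supplied by Roche from induction to maintenance". Protocol 7 counts four parts in the treatment period: induction, conditioning, "maintenance : 3 years", and a further 3 years on demand.

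The output meant to deliver the duration is Table 5.99.1-3, headed Treatment intake duration, on the Safety Set. Its footnote defines it as "the time between the 1st intake of any induction drugs and the last intake of any induction drugs". The induction drugs are dexamethasone, cytarabine and the platinum agent as well as obinutuzumab.

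For the later periods, the SAP tabulates total dose and percentage of planned dose (PPD) at ASCT, in maintenance (Table 5.9-4) and on demand (Table 5.9-5). It has no duration table for any of them. According to its document history, SAP version 2.0 was issued to add on-demand maintenance, and SAP 4.3 places all secondary endpoints in the final analysis.

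**The concern.** The endpoint promised is the duration of study-drug treatment. The rule that produces it stops at the end of induction and follows any induction drug, not obinutuzumab. Both documents name tolerability of obinutuzumab at induction and then on demand as a secondary objective. Adverse events are tabulated for the maintenance period (Tables 5.101-1 and 5.101-2) and by on-demand onset (Table 5.101-5).

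To read those counts, one needs to know how long patients were on the drug. This matters most in the on-demand period, where dosing depends on MRD and will differ widely between patients. Followed as written, the SAP produces a duration only for the first two months or so.

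**Working it through.** One month is taken as 30.4375 days.

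**Reproducing the plan's own figures**
- Protocol 10.2.1: "Patients will receive 4 cycles of GA-DHAP every 21 days". 4 × 21 = 84 days = 12 weeks, the induction length in Protocol 7.
- Obinutuzumab infusions in induction: 3 in cycle 1 plus 1 in each of cycles 2 to 4 = 6. 6 × 1000 mg = 6000 mg, the expected induction dose in the SAP.

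**What Table 5.99.1-3 will show**
- Cycle 4 day 1 falls 3 × 21 = 63 days after cycle 1 day 1. The last induction drug is dexamethasone on cycle 4 day 4: 63 + 3 = 66 days. 66 / 30.4375 = 2.2 months.
- With three one-week delays: 66 + 21 = 87 days = 2.9 months.
- If the COP pre-phase counted as an induction drug (5 days plus a 7-day gap): 66 + 12 = 78 days = 2.6 months. The footnote does not say whether it counts.

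**What the obinutuzumab schedule spans** (Protocol 10.2.2 and 10.2.3)

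| Step | Shortest | Longest |
|---|---|---|
| Cycle 1 day 1 to cycle 4 day 1 | 63 d | 63 d |
| To start of conditioning (4 to 8 weeks) | 28 d | 56 d |
| To day 1 of ASCT (0 or 8 d, depending on what day 1 means) | 0 d | 8 d |
| Subtotal | 91 d = 3.0 months | 127 d = 4.2 months |
| To start of maintenance (2 to 3 months) | 5.0 months | 7.2 months |
| End of fixed maintenance (+36 months) | 41.0 months | 43.2 months |
| End of on-demand period (+36 months) | 77.0 months | 79.2 months |

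The table's 2.2 months is therefore 5.0 to 5.3% of the span to the end of fixed maintenance, and 2.7 to 2.8% of the calendar maximum.

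**Whether another SAP output gives time on drug**
- Tables 5.9-4 and 5.9-5: total dose and PPD only. The dose is headed in mg/m² although obinutuzumab is a flat 1000 mg.
- Table 4.7-3 (patients at each timepoint): visit counts on the Included Set. MRD-negative patients are also seen in the on-demand period without receiving the drug.
- Premature treatment discontinuation (SAP 5.2.1): time from inclusion, for discontinuers only.
- Study duration (Table 5.1.2-3) and follow-up (SAP 5.1.3): both run to last contact.
- Tables 5.9-1 and 5.9-2 on cycles performed: the listed cycles are the four induction cycles.

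None gives time on obinutuzumab after induction.

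**The smaller point: any induction drug**

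If obinutuzumab stopped early and DHAP ran on schedule to cycle 4 day 4, the excess is 66 days minus the day of the last obinutuzumab infusion, counted from cycle 1 day 1:
- last infusion cycle 1 day 1: 66 − 0 = 66 days
- cycle 1 day 15: 66 − 14 = 52 days
- cycle 2 day 1: 66 − 21 = 45 days
- cycle 3 day 1: 66 − 42 = 24 days
- on-schedule completer: 66 − 63 = 3 days

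**The case against.** **The footnote is honest.** It says induction, and the table sits under a heading on cycles, after two tables on the induction cycles. A reader might infer that the final report would misstate obinutuzumab duration by an order of magnitude. The documents do not support that. The table is a correct induction duration under too general a title. The fault is that it is the only duration table.

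**Other outputs help.** Protocol 10.3.1.2.3 allows no dose reductions, so total dose at a flat 1000 mg tracks the number of infusions closely. Discontinuation dates are listed, and fixed maintenance has a set length for those who complete it. This stands in part: exposure after induction is not unreported. But a dose total does not give time on drug when on-demand treatment can stop and restart.

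**The long figure is a ceiling.** It would be tempting to set 2 months against about 6.5 years as if that were typical. On-demand obinutuzumab is given only to MRD-positive patients. Those who stay negative end at about 41 to 43 months.

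**Time credited after obinutuzumab has stopped.** A reader might infer that the table will do this for patients stopped by a grade 4 infusion reaction. Protocol 10.5.1 says only "Stop infusion and discontinue therapy" and does not say whether DHAP goes on. The text on suspected PML (Protocol 10.3.4) asks only that stopping or reducing chemotherapy be considered, so the possibility is open. The documents give no frequency, the excess is at most about 66 days on schedule, and the by-cycle dose table would still show missed obinutuzumab.

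**It is descriptive.** No primary, PFS, OS or response result depends on this table, and the adverse-event shells show counts and percentages, not exposure-adjusted rates. This limits the consequence but does not deliver the promised endpoint.

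**Conclusion.** The concern holds. The SAP promises the duration of study-drug treatment but defines its only duration table to end with the last induction drug. For a patient completing induction on schedule, the table shows about 2.2 months. The drug is scheduled to about 41 to 43 months through fixed maintenance, and to a calendar maximum of about 77 to 79 months only for patients dosed late in the on-demand period. The final report would give no time on obinutuzumab beside maintenance and on-demand adverse events.

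These figures assume on-schedule dosing and run to the planned end of each period. Delays, or a last infusion somewhat before the end of a period, move them by weeks to a couple of months and do not change the conclusion. Crediting time after obinutuzumab has stopped is a secondary point, capped at about 66 days on schedule and of unknown frequency.

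**What to change.** 1. Retitle Table 5.99.1-3 *Duration of induction (any GA-DHAP drug)*, and state whether COP pre-phase drugs count.
2. Add a table of obinutuzumab treatment duration by period (induction, ASCT, maintenance, on-demand), with the number of infusions per period. Base it on obinutuzumab dates only, which also settles the any-induction-drug point.
3. For the on-demand period, sum the treated episodes among patients given at least one on-demand dose, and state how many patients that is.
4. If an overall figure is wanted, build it from time on drug by period. A plain first-to-last span would count drug-free intervals between on-demand episodes, so it should be shown only if labelled as including them.

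The cost is SAP wording and a few extra table rows. The dosing records are those already used for the SAP's obinutuzumab dose tables. No data collection, treatment rule or efficacy analysis changes.

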## 5.9.2 Dose

**Table 5.9-3 GA101 administration by cycle during induction period – Safety set**

	Cycle 1			Cycle 2		Cycle 3		Cycle 4	
	Day 1 N=XX	Day 8 N=XX	Day 15 N=XX	Day 1 N=XX					
Total dose taken (mg/m^2)									
N	XX	XX	XX	XX	XX	XX	XX	XX	XX
Missing	XX	XX	XX	XX	XX	XX	XX	XX	XX
Mean (SD)	XX.X (XX.XX)	XX.X (XX.XX)	XX.X (XX.XX)	XX.X (XX.XX)	XX.X (XX.XX)	XX.X (XX.XX)	XX.X (XX.XX)	XX.X (XX.XX)	XX.X (XX.XX)
Median	XX.X	XX.X	XX.X	XX.X	XX.X	XX.X	XX.X	XX.X	XX.X
Q1 ; Q3	XX ; XX	XX ; XX	XX ; XX	XX ; XX	XX ; XX	XX ; XX	XX ; XX	XX ; XX	XX ; XX
Min ; Max	XX ; XX	XX ; XX	XX ; XX	XX ; XX	XX ; XX	XX ; XX	XX ; XX	XX ; XX	XX ; XX
PPD (%)									
N	XX	XX	XX	XX	XX	XX	XX	XX	XX
Missing	XX	XX	XX	XX	XX	XX	XX	XX	XX
Mean (SD)	XX.X (XX.XX)	XX.X (XX.XX)	XX.X (XX.XX)	XX.X (XX.XX)	XX.X (XX.XX)	XX.X (XX.XX)	XX.X (XX.XX)	XX.X (XX.XX)	XX.X (XX.XX)
Median	XX.X	XX.X	XX.X	XX.X	XX.X	XX.X	XX.X	XX.X	XX.X
Q1 ; Q3	XX ; XX	XX ; XX	XX ; XX	XX ; XX	XX ; XX	XX ; XX	XX ; XX	XX ; XX	XX ; XX
Min ; Max	XX ; XX	XX ; XX	XX ; XX	XX ; XX	XX ; XX	XX ; XX	XX ; XX	XX ; XX	XX ; XX
PPD (%)									
< 75%	XX (XX.X%)	XX (XX.X%)	XX (XX.X%)	XX (XX.X%)	XX (XX.X%)	XX (XX.X%)	XX (XX.X%)	XX (XX.X%)	XX (XX.X%)
[75% - 90%]	XX (XX.X%)	XX (XX.X%)	XX (XX.X%)	XX (XX.X%)	XX (XX.X%)	XX (XX.X%)	XX (XX.X%)	XX (XX.X%)	XX (XX.X%)
[90% - 110%]	XX (XX.X%)	XX (XX.X%)	XX (XX.X%)	XX (XX.X%)	XX (XX.X%)	XX (XX.X%)	XX (XX.X%)	XX (XX.X%)	XX (XX.X%)
[110% - 125%]	XX (XX.X%)	XX (XX.X%)	XX (XX.X%)	XX (XX.X%)	XX (XX.X%)	XX (XX.X%)	XX (XX.X%)	XX (XX.X%)	XX (XX.X%)
>= 125%	XX (XX.X%)	XX (XX.X%)	XX (XX.X%)	XX (XX.X%)	XX (XX.X%)	XX (XX.X%)	XX (XX.X%)	XX (XX.X%)	XX (XX.X%)

Expected dose per cycle for GA101 : 1000mg D1 + 1000mg D8 + 1000mg D15 of cycle 1.

Total dose is the sum of dose administered during one day of a cycle.

PPD = (Total dose taken/total dose expected)/100

**Table 5.9-2 GA101 administration during induction period – Safety set**

	Safety set N=XX
Total dose taken (mg/m^2)	
N	XX
Missing	XX
Mean (SD)	XX.X (XX.XX)
Median	XX.X
Q1 ; Q3	XX ; XX
Min ; Max	XX ; XX
PPD (%)	
N	XX
Missing	XX
Mean (SD)	XX.X (XX.XX)
Median	XX.X
Q1 ; Q3	XX ; XX
Min ; Max	XX ; XX
PPD (%)	
< 75%	XX (XX.X%)
[75% - 90%]	XX (XX.X%)
[90% - 110%]	XX (XX.X%)
[110% - 125%]	XX (XX.X%)
>= 125%	XX (XX.X%)

Expected total dose during induction for GA101 : 6000mg.

Total dose is the sum of dose administered during induction.

PPD = (Total dose taken/total dose expected)/100

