10.3.1.2 Management of hematological toxicity in patients receiving GA101

10.3.1.2.1 **Neutropenia**

Cases of Grade 3 or 4 neutropenia, including febrile neutropenia, have been reported with GA101 administration. Grade 3 or 4 neutropenia has predominantly been observed in patients with CLL. Patients who experience Grade 3 or 4 neutropenia should be monitored until neutrophil values return to at least Grade 2. Use of granulocyte colony-stimulating factors (G-CSF) has been found to result in a rapid normalization of neutrophils, similar to what has been observed in patients treated with rituximab. The use of G-CSF is allowed for treatment of neutropenia in this study. Primary prophylaxis with G-CSF is recommended according to the American Society of Clinical Oncology (ASCO), EORTC, and European Society for Medical Oncology (ESMO) guidelines, namely for patients who are \geq 60 years old and/or with co-morbidities (Lyman et al. 2004). The use of G-CSF is mandatory in Cycle 1 for all patients.

10.3.1.2.2 **Thrombocytopenia**

Severe and life threatening thrombocytopenia including acute thrombocytopenia (occurring within 24 hours after the infusion) has been observed during treatment with GA101. Fatal haemorrhagic events have also been reported in patients treated with GA101. It seems that the first cycle is the greatest risk of haemorrhage in GA101-treated patients. A clear relationship between thrombocytopenia and haemorrhagic events has not been established. Patients treated with concomitant medication, which could possibly worsen thrombocytopenia related events such as platelet inhibitors and anticoagulants, may be at greater risk of bleeding. Patients should be closely monitored for thrombocytopenia, especially during the first cycle; regular laboratory tests should be performed until the event resolves, and dose delays should be considered in case of severe or life-threatening thrombocytopenia. Transfusion of blood products (i.e. platelet transfusion) according to institutional practice is at the discretion of the treating physician.

10.3.1.2.3 **GA101 dose adjustments**

There will be no dose reductions for GA101 (1000 mg). During Cycle 1, the Day 8 and D15 doses of GA101 may be administered whatever the neutrophil count if there is no evidence of infection or bleeding and if platelet count is $>50 \times 10^9 / L$.

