## 7.3 Appendix A: Calculation of total dose and PPD

Percentage of Planned Dose is defined as follow:

$$PPD = \frac{\text{Total dose taken in mg/m}^2}{\text{Total dose expected in mg/m}^2} \times 100$$

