**Table 7.6-1 Calculation of total dose taken and expected**

	Total dose taken	Total dose expected
Cycle i	Sum of doses administered during Cycle i	Sum of doses expected during Cycle i
Cycle i - Cycle j	Sum of doses administered from Cycle i to Cycle j	Sum of doses expected from Cycle i to Cycle j when administered

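### The SAP defines GA101 percentage of planned dose inconsistently, and the choice of induction denominator changes the dose class of patients who stop induction early

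*SAP*

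**What the plan says.** SAP 3.4 lists percentage of planned dose among its three exposure measures, and treatment exposure is part of the primary criterion analysis (SAP 4.2; Protocol 15.5). The rule for computing PPD appears in two places.

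- **SAP 5.9.2.** Five GA101 tables (induction by cycle, induction overall, ASCT, maintenance, maintenance on-demand) carry the footnote "PPD = (Total dose taken/total dose expected)/100". Each labels dose taken in mg/m², while the footnotes give the expected dose in mg. For induction overall (Table 5.9-2, GA101 administration) the footnote is "Expected total dose during induction for GA101 : 6000mg". PPD is then grouped into five classes, with cut-points at 75%, 90%, 110% and 125%.
- **SAP 7.3, Appendix A.** It opens with "Percentage of Planned Dose is defined as follow" and gives the ratio multiplied by 100, with both terms in mg/m². Table 7.6-1 sets the denominator. For a single cycle it is the dose expected in that cycle, without qualification. For a run of cycles it is "Sum of doses expected from Cycle i to Cycle j when administered".

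Protocol 10.1.4 states "Obinutuzumab will be administered at the flat dose of 1000mg", and Protocol 10.3.1.2.3 rules out reducing that dose. The SAP does not say whether the footnotes or Appendix A prevail.

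**The concern.** Because GA101 is not dose-reduced, a low induction total arises mainly when infusions are omitted or left incomplete, or when induction ends early. PPD is the summary that shows how much of the planned obinutuzumab lies behind the post-induction MRD result. A denominator restricted to cycles given takes early stopping out of that summary, whereas a fixed planned total keeps it in. Two programmers who both follow the SAP could therefore report different dose classes from identical data.

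The later periods are also open. The maintenance and on-demand footnotes give a schedule but no total. They have no rule for patients who stop early or never enter the period, although the tables are on the Safety Set.

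**Working it through.** **Inputs.** GA101 1000 mg on days 1, 8 and 15 of cycle 1, and 1000 mg on day 1 of cycles 2 to 4 (Protocol 10.2.1; SAP Tables 7.6-2 and 7.6-3). Class limits are from SAP 5.9.2.

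**The plan's own figure.** 3 × 1000 + 3 × 1000 = 6000 mg. This reproduces the total in Table 5.9-2.

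**Step 1, the factor.** For a fully dosed patient the footnote gives (6000/6000)/100 = 0.01, and Appendix A gives (6000/6000) × 100 = 100. The rows are headed in percent and the classes are percentages, so only the second is workable.

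**Step 2, the units.** With mg/m² above and below, as Appendix A writes it, body surface area (BSA) cancels: (6000/BSA)/(6000/BSA) × 100 = 100%. The same holds with mg above and below. The label is wrong for a flat dose, but PPD changes only if the two units are mixed.

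**Step 3, the denominator.** Using × 100 and one unit, take a patient who receives every planned dose and stops after cycle *k*. The multi-cycle row of Table 7.6-1 is read as counting cycles that were given.

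| Stops after cycle | Taken (mg) | Fixed 6000 mg | Class | Cycles given | Class |
|---|---|---|---|---|---|
| 1 | 3000 | 3000/6000 = 50.0% | <75% | 3000/3000 = 100% | 90-110% |
| 2 | 4000 | 4000/6000 = 66.7% | <75% | 4000/4000 = 100% | 90-110% |
| 3 | 5000 | 5000/6000 = 83.3% | 75-90% | 5000/5000 = 100% | 90-110% |
| 4 | 6000 | 6000/6000 = 100% | 90-110% | 6000/6000 = 100% | 90-110% |

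**Step 4, doses omitted within a started cycle.** A patient who misses days 8 and 15 of cycle 1 but completes four cycles takes 4 × 1000 = 4000 mg. If the Appendix A qualifier works by cycle, all four cycles were given, the denominator is 6000 mg under both rules, and PPD is 66.7% either way. If it worked by individual dose, the denominator would be 4000 mg and PPD 100%. The single-cycle row has no qualifier, which favours the by-cycle reading, but the SAP does not say so.

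**The case against.** The strongest reply is that little of this would reach a published table. Division by 100 under a row headed in percent is plainly a slip, and Appendix A's like-for-like units make BSA cancel. Early stopping is also visible elsewhere: cycles performed, number of cycles and treatment duration (SAP 5.9.1), GA101 by cycle and day (5.9.2), and discontinuation by reason and period (5.2.1). PPD enters no endpoint, analysis set or test. A planned-dose denominator and a cycles-started denominator are both legitimate; they answer different questions.

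Most of that stands, and it rules out several stronger readings that a reader might infer:

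- *That the footnote will put every patient below 75%.* It does so only if programmed literally, which the percent headings and Appendix A make implausible.
- *That fully dosed patients will show about 56%.* This needs mg/m² divided by mg. At an assumed BSA of 1.8 m² the result is 100/1.8 = 55.6% (71.4% to 41.7% for 1.4 to 2.4 m²). Appendix A's formula excludes that mixture, and the documents give no BSA distribution.
- *That Appendix A gives nearly everyone about 100%.* On the by-cycle reading, omitted day 8 and day 15 doses still lower PPD.
- *That patients move between opposite extremes.* On any sensible reading the shift is from a low class to the on-target class, never from below 75% to 125% or more.

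The reply does not remove the denominator conflict. Both rules are written in the current SAP, neither is an obvious slip, and they give different answers for anyone who stops induction early. That other tables show early stopping does not settle which PPD is reported.

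**Conclusion.** The PPD definition is wrong as written in its factor and unit label, and internally inconsistent in its induction denominator. Only the denominator changes results on a sensible reading. For full dosing through cycle 1, 2 or 3, the two rules differ by 50.0, 33.3 or 16.7 percentage points (100 minus 50.0, 66.7 or 83.3), and the dose class changes each time. Patients who complete four cycles are unaffected if the Appendix A qualifier works by cycle. The number of patients concerned is not known from the documents.

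A reader might infer that the main efficacy conclusion is at risk. It is not: the decision rule of 46 or more MRD-negative among 70 evaluable patients makes no use of PPD. The consequence is confined to descriptive exposure tables. It is still worth correcting, because exposure is reported with the primary result.

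**What to change.** In SAP 5.9.2 and Appendix A:

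1. Correct the five footnotes to multiply by 100.
2. Report GA101 in mg throughout, including the row labels and the Appendix A formula as applied to GA101.
3. Use one named induction denominator in both places: the 6000 mg already stated in Table 5.9-2, with omitted doses counted as zero.
4. Show PPD over cycles started as a second, labelled line, and state that it works by cycle.
5. For ASCT, maintenance and on-demand, compute PPD among patients who entered the period and state the denominator used.

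If induction exposure outputs already exist, the report should say which rule was programmed.

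The cost is footnote and appendix wording plus re-running descriptive tables on the same data. The downside is that, if the Appendix A rule would otherwise have been used, reported PPD will be lower for patients who stop induction early. The second line keeps the other quantity visible. The change redefines a summary statistic and implies nothing about dosing.
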